**Secondary research questions:**

- 1) Compared to the control group, does this therapeutic approach achieve drug-free diabetes remission in a higher proportion of patients than standard diabetes therapy at 36, 48 and 64 weeks after randomization?
- 2) Compared to the control group, does this therapeutic approach achieve drug-free HbA1C <6.0% in a higher proportion of patients than standard diabetes therapy at 24, 36, 48 and 64 weeks after randomization?
- 3) Compared to the control group, does this therapeutic approach achieve drug-free diabetes regression in a higher proportion of patients than standard diabetes therapy at 24, 36, 48 and 64 weeks after randomization? Diabetes regression is defined as HbA1C 6.5-6.9% off glucose-lowering agents for at least 12 weeks.
- 4) What HbA1C levels are achieved in the intervention group and the control group at 12, 24, 36, 48 and 64 weeks after randomization?
- 5) What rates of hypoglycemia are observed in the intervention group and the control group during 64 weeks of follow-up?
- 6) What is the change in weight, body mass index (BMI), waist circumference and waist/hip ratio from baseline to 12, 24, 36, 48 and 64 weeks in the intervention group and the control group?
- 7) Are age, gender, ethnicity, diabetes duration, smoking, family history of diabetes, baseline BMI, waist circumference, HbA1C or fasting plasma glucose (FPG) determinants of diabetes remission at 24 weeks after randomization?

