## **2.3 Safety objective**

To determine rates of severe and non-severe hypoglycemic episodes in the treatment groups during 64 weeks of follow-up.

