## 4.2 Exclusion criteria

- 1) current use of insulin therapy;
- 2) history of hypoglycemia unawareness, or severe hypoglycemia requiring assistance;
- 3) history of end-stage renal disease or renal dysfunction as evidenced by eGFR < 60 mL/min/1.73 m^2 by MDRD formula;
- 4) history of lactic acidosis or diabetic ketoacidosis;
- 5) active liver disease or elevated alanine transferase (ALT) levels  $\geq 2.5$  times upper limit of normal at the time of enrollment;
- 6) history of bladder cancer or undiagnosed hematuria;
- 7) history of breast cancer;
- 8) history of polycythemia;
- 9) evidence of volume depletion or hypotension (systolic blood pressure < 90 mmHg);
- 10) systolic blood pressure > 180 mmHg or diastolic blood pressure > 105 mmHg;
- 11) diagnosed cardiovascular disease (unless cleared for a moderate intensity exercise program by a specialist) including:
  - a. any history of acute coronary syndrome, hospitalization for unstable angina, myocardial infarction, or revascularization with coronary artery bypass grafting or percutaneous coronary intervention;
  - b. other evidence of coronary artery disease;
  - c. peripheral vascular disease, valvular heart disease, cardiomyopathy, aortic dissection, tachyarrhythmias, bradyarrhythmias, prior stroke or TIA;
  - d. prior hospitalization for heart failure; or
  - e. ECG findings concerning for ischemic heart disease (i.e. pathological Q-waves, ST-segment-T-wave abnormalities in contiguous leads, left anterior hemiblock, left bundle branch block, second or third degree atrioventricular block).
- 12) dependence on oxygen;
- 13) history of any disease requiring frequent intermittent or continuous systemic glucocorticoid treatment;
- 14) history of bariatric surgery, or planned bariatric surgery in the next 1.5 years;
- 15) history of any major illness with a life expectancy of < 3 years;
- 16) history of injury or any other condition that significantly limits participant's ability to achieve moderate levels of physical activity;
- 17) any history of excessive alcohol intake, acute or chronic;

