#### **5.3.1.4 Monitoring during the induction phase of the trial**

At the first study visit, intervention group participants will be taught how to self-monitor capillary blood glucose and how to inject insulin. Participants and their families will also be taught how to recognize and treat hypoglycemia. During the intensive metabolic intervention, participants will be asked to monitor glucose at least twice daily at varying times, including before and 2 hours after meals, and during exercise. Research staff will meet with intervention group participants once a week during the first 6 weeks of the trial and will contact them by telephone at least once a week between visits to review glucose readings, medication titration, medication adherence and side effects (see schedule in Table 1 in Appendix A). Research staff will continue to meet with intervention group participants every 2 weeks and will contact them by telephone every other week during week 7-12 of the trial. All hypoglycemic episodes will be documented and reviewed with an investigator promptly. Glucose-lowering therapy will be adjusted accordingly.

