#### **6.2.2 Other outcomes**

Symptomatic and severe hypoglycemic episodes will be measured in both treatment groups. Anthropometric measures including height (at the screening visit only), body weight, waist and hip circumference will be measured in all participants (see schedule in Appendix A Table 1). Body mass index will be reported in kg/m^2. Waist circumference will be measured around the exposed abdomen at the level of the top of the iliac crest at the end of a normal expiration. Hip circumference will be measured as the maximal circumference over the buttocks over light clothing.

In addition, 2 six-point glucose profiles will be collected during the 6th and 12th week after randomization. Each six-point glucose profile will include pre-meal and 2-hour post-meal readings taken on the same day. To standardize this measure, all participants will be provided with identical glucometers which will be calibrated regularly. Mean fasting and post-meal glucose values will be calculated for each participant from the two glucose profiles.

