## 6.3 Safety

### 6.3.1 Safety variables

Information on the following prespecified safety outcomes will be prospectively collected in all study participants during the trial:

- 1) Death (and cause of death as determined by a physician);
- 2) Non-fatal myocardial infarction or angina resulting in hospitalization or emergency room admission;
- 3) Non-fatal stroke or transient ischemic attack diagnosed by a physician;
- 4) Heart failure resulting in hospitalization or emergency room admission;
- 5) Resuscitated cardiac arrest or life-threatening arrhythmia (including documented or presumed ventricular fibrillation, sustained ventricular tachycardia, asystole, or pulseless electrical activity);
- 6) Cardiogenic shock diagnosed by a physician;
- 7) Diabetic ketoacidosis or hyperglycemic hyperosmolar state diagnosed by a physician;
- 8) Documented new fractures;
- 9) Newly diagnosed cancers;
- 10) Genitourinary infections diagnosed by a physician;
- 11) Moderate (eGFR 30-60 mL/min/1.73 m^2 by MDRD formula) or severe (eGFR <30 mL/min/1.73 m^2) renal dysfunction;
- 12) Symptomatic and severe hypoglycemic events (see below for definitions);
- 13) Hospital or emergency room admissions (and reasons for admission).

Participants will be asked to record all hypoglycemic episodes and symptoms in a diary that will be provided to them. Moreover, they will be explicitly asked about any episodes of symptomatic or severe hypoglycemia during every visit and telephone follow-up.

*Symptomatic hypoglycemia* is defined as an event with clinical symptoms consistent with hypoglycemia, based on data recorded in the participant's diary. These will be further categorized as confirmed (i.e. with a concomitant home glucose reading  $\leq 3.0$  mmol/L) or unconfirmed. Symptomatic hypoglycemic events and those that result in alteration of any of the study drugs will be recorded.

*Severe hypoglycemia* is defined as an event with clinical symptoms consistent with hypoglycemia in which the participant required the assistance of another person, and one of the following: (i) the event was associated with a documented self-measured or laboratory plasma glucose level  $\leq 2.0$  mmol/L; or (ii) the event was associated with prompt recovery after oral carbohydrate, intravenous glucose, or glucagon administration. Any episode of severe hypoglycemia will be recorded and reviewed within one working day.

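### The hypoglycemia outcome requires symptoms but the safety objective does not, so a symptom-free home reading at or below 3.0 mmol/L falls in no outcome category

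*Combined protocol and SAP*

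**What the plan says.** The aims carry no symptom condition. Section 2.3, the only safety objective, reads "To determine rates of severe and non-severe hypoglycemic episodes in the treatment groups during 64 weeks of follow-up". Secondary question 5 in section 1.2 asks "What rates of hypoglycemia are observed in the intervention group and the control group during 64 weeks of follow-up". The term non-severe is not defined anywhere.

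The measured outcome is narrower. Section 6.2.2 says "Symptomatic and severe hypoglycemic episodes will be measured in both treatment groups", and item 12 of the safety list in section 6.3.1 names the same two classes. In section 6.3.1, symptomatic hypoglycemia "is defined as an event with clinical symptoms consistent with hypoglycemia, based on data recorded in the participant's diary". A concomitant home reading at or below 3.0 mmol/L makes such an event confirmed; otherwise it is unconfirmed. Severe hypoglycemia requires symptoms, another person's help, and either a glucose at or below 2.0 mmol/L or prompt recovery after treatment.

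Several collection rules are wider than the outcome:
- Section 5.3.1.4, for the intervention group during induction: "All hypoglycemic episodes will be documented and reviewed with an investigator promptly".
- Section 6.3.1 has the diary hold all episodes as well as symptoms, and also records events that lead to a change in a study drug.
- Table 1 in Appendix A schedules review of home readings through week 64.

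Section 6.2.2 adds glucose profiles at weeks 6 and 12, for which "all participants will be provided with identical glucometers which will be calibrated regularly". Their only stated summary is mean fasting and post-meal glucose per participant.

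**The concern.** The objective and the outcome do not cover the same events. A symptom-free home reading of 2.6 mmol/L is below the protocol's own cut-off, yet it is neither a symptomatic nor a severe event. No planned table would show it, and a mean over a profile can hide it.

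This matters more here than in many trials. The trial is open-label, and the retained outcome starts from symptoms that unblinded participants report. Insulin is titrated by the participant to a fasting 4.0-5.3 mmol/L (section 5.3.1.2). The protocol itself treats missing warning symptoms as a hazard, since it excludes people with "history of hypoglycemia unawareness, or severe hypoglycemia requiring assistance". A meter-based count would complement the self-reported one, and the data for it are already to be collected.

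Two smaller ambiguities go with this. Because non-severe is undefined, the symptomatic count could be published under that name. The unconfirmed class also merges an event with no reading, one at 3.4 mmol/L and one at 7 mmol/L, so missing data cannot be told apart from a reading that contradicts the event.

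**Working it through.** The documents give no expected hypoglycemia rate, so there is no planned figure to reproduce. The main check is on the text.

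**1. Where a symptom-free reading at or below 3.0 mmol/L would go**

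| Rule | Symptom condition? | Includes the reading? |
|---|---|---|
| Objective, 2.3 | None stated | Unclear: non-severe undefined |
| Question 5, 1.2 | None stated | Unclear: no definition |
| Outcome, 6.2.2 and 6.3.1 item 12 | Yes, in both classes | No |
| Confirmed/unconfirmed split, 6.3.1 | Applies to symptomatic events | No |
| Profile summary, 6.2.2 | Not applicable | Only within a mean |
| Diary, 6.3.1 | None stated | Possibly: episode undefined |
| Questioning at contacts, 6.3.1 | Symptomatic or severe only | No |
| Drug-alteration clause, 6.3.1 | Can be read either way | Only if a study drug is changed |
| Investigator review, 5.3.1.4 | None stated | Possibly: episode undefined |

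The gap is in the outcome rows. The collection and review rows do not exclude the reading, but they do not settle its status either.

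**2. When a rate would be understated**

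Let f be the share of all low episodes that have no symptoms. Then all low episodes / counted episodes = 1/(1 - f). The documents do not give f, so these values are assumptions:
- f = 0: 1.00
- f = 0.10: 1/0.90 = 1.11
- f = 0.25: 1/0.75 = 1.33
- f = 0.50: 1/0.50 = 2.00

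The ratio applies only to a rate presented as covering all low episodes. It does not apply to a rate labelled symptomatic. Unconfirmed symptomatic events are also counted, which pushes the reported rate the other way.

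**3. Why the source of readings matters**

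In induction, testing at least twice daily is specified for the intervention group (5.3.1.4). No frequency is given for controls (5.3.2). At the minimum, the intervention arm has 2 readings x 84 days x 76 participants = 12,768 readings. If 0.5% to 1% were symptom-free and at or below 3.0 mmol/L (an assumed range; zero is equally compatible with the documents), that is 64 to 128 readings, or 0.84 to 1.68 per participant. There is no matching control denominator, so these counts cannot be compared between arms.

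Scheduled review is unequal too. Counting the SMBG review row of Table 1 up to week 12, the intervention group has 11 + 1 + 5 + 1 = 18 reviews and the control group has 2 (weeks 6 and 12).

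The profiles do not have this problem, because Table 1 marks them for both groups. Reading its footnote as two profiles at each of weeks 6 and 12, each participant has 2 x 6 x 2 = 24 readings, at most 24 x 76 = 1,824 per arm. At the same assumed 0.5% to 1%, that is about 9 to 18 readings in the intervention arm. Section 6.2.2 could also be read as one profile per week: 12 readings per participant, at most 912 per arm, and about 5 to 9 low readings. Either way the schedule is equal between arms and the counts are sparse.

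**The case against.** The strongest defence is that symptomatic and severe hypoglycemia is a stated, usable outcome, and that the rest of the protocol deals with silent lows. Much of this stands.

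- **Review.** A reader might infer that symptom-free lows escape the review of all episodes. The documents do not support that. Section 5.3.1.4 sets no symptom condition, the diary asks for all episodes, and home readings are reviewed at contacts through week 64. Staff would be expected to see the 2.6 mmol/L reading in the example. What remains is that episode is undefined, so sites could differ, and that this review is described only for the intervention group in induction.
- **Recording.** A reader might infer that nothing is recorded without symptoms. The clause in section 6.3.1 on events that alter a study drug can be read to include symptom-free lows, and section 6.3.3.1 documents adverse events that change a dose. Neither creates an outcome category, and Table 1 starts study medications only in the intervention group.
- **Understatement.** A reader might infer that the plan understates harm. A rate labelled symptomatic is not understated by leaving out symptom-free readings, and excluding people with a history of unawareness should reduce the number of silent lows.
- **Remedy.** Adding every low home reading to the non-severe rate would build unequal detection into the comparison. This is correct, and it is why the category below stays separate.

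Secondary outcomes are only hypothesis-generating (section 11.2), so the primary conclusion and the sample size are untouched. That limits the weight of the point, but it does not align the outcome with the objective.

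**Conclusion.** The mismatch holds. Section 2.3 and question 5 are wider than the outcome in sections 6.2.2 and 6.3.1, and a symptom-free home reading at or below 3.0 mmol/L enters no prespecified category. The tempting stronger conclusions, that such readings go unreviewed or that the hypoglycemia rate is understated, are not supported. The first conflicts with the wording of section 5.3.1.4. The second would be true only if the symptomatic count were reported as the non-severe rate and some lows were symptom-free.

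The size cannot be derived from the documents. The ratios of 1.00 to 2.00 and the counts of low readings rest on assumed shares and show direction and scale only. The equal schedule of profiles rests on Table 1; the number per participant is 24 or 12, depending on how the text is read. The point is a cheap improvement to safety reporting in an open-label insulin trial and does not threaten the primary analysis.

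**What to change.** 1. In section 6.3.1, add a separately reported category: glucose at or below 3.0 mmol/L regardless of symptoms. Do not pool it into the symptomatic rate.
2. In section 11.2, compare this category between arms only on the week-6 and week-12 profiles, as the number and proportion of participants with at least one such reading. Give the number of profile readings obtained per arm, and state whether one or two profiles are due at each week.
3. Report other low home readings descriptively, with the number of readings per arm as the denominator.
4. In section 2.3, state that non-severe means symptomatic events, confirmed or unconfirmed, that do not meet the severe definition, plus the new category shown on its own line.
5. In section 5.3.1.4, state whether episode includes symptom-free readings at or below the cut-off, and reconcile the wording with section 6.3.1.
6. Report unconfirmed events by whether a reading was taken, with its value if so.

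The cost is protocol and case report form wording, transcription of readings already collected, and one small table. The counts will be sparse, and the safety picture may look less favourable. There is no new measurement and no change to any treatment rule.

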### **6.3.2 Definitions of adverse events**

#### **6.3.2.1 Adverse events**

An adverse event is any untoward medical occurrence that occurs in a person during the period of observation in a clinical study. It does not necessarily have to have a causal relationship with any treatment administered as part of that study. An adverse event can therefore be any unfavorable and unintended sign, symptom or disease, whether or not it is considered related to any medicinal product being taken at the time the event occurs.

#### **6.3.2.2 Serious adverse events (SAEs)**

A *serious adverse event* is one that at any dose (including overdose):

- 1) results in death;
- 2) is life-threatening (i.e. participant was at immediate risk of death at the time of the serious adverse event; it does not refer to an adverse event that hypothetically might have caused death if it were more severe);
- 3) requires inpatient hospitalization or prolongation of existing hospitalization;
- 4) results in persistent or significant disability or incapacity (i.e. there is a substantial disruption of a person's ability to carry out normal life functions);
- 5) causes a congenital anomaly or birth defect;
- 6) is an important medical event (Important medical events that may not be immediately life-threatening or result in death or hospitalization but may jeopardize the participant or may require intervention to prevent one of the other outcomes listed in the definition above will be also considered serious. Examples of such events include allergic bronchospasm requiring intensive treatment in an emergency room or at home, blood dyscrasias or convulsions that do not result in participant hospitalization, or the development of drug dependency or drug abuse. A diagnosis of cancer during the course of a treatment will also be considered as medically important.)

#### **6.3.2.3 Clarification of the difference in meaning between “severe” and “serious”**

The term “severe” is often used to describe the intensity (severity) of a specific event (as in mild, moderate, or severe headache). The event itself, however, may be of relatively minor medical significance (such as severe headache). This is not the same as “serious”, which is

based on the outcome or action criteria usually associated with events that pose a threat to life or functioning. Seriousness (not severity) serves as a guide for defining regulatory reporting obligations.

### **6.3.3 Documentation and reporting of adverse events, pregnancies and overdoses**

#### **6.3.3.1 Documentation and reporting of non-serious adverse events**

Any adverse event resulting in a change in dose (including temporary withholding) of any of the study medications (insulin glargine, metformin and Forxiga) will be documented on case report forms. Examples of such events could include gastrointestinal complaints or genitourinary infections. All changes in the medication dose will be recorded.

#### **6.3.3.2 Documentation and reporting of serious adverse events (SAEs)**

Whenever an investigator judges an event to be an SAE, he/she will complete an SAE case report form within one working day and will notify the PHRI Project Office as well as local REB as per REB requirements. All SAEs will be reported by the PHRI to AstraZeneca ( $\pm$  Health Canada). If the event meets criteria of (i) serious and (ii) related to insulin glargine, metformin or Forxiga and (iii) unexpected, it will be subject to expedited reporting to AstraZeneca ( $\pm$  Health Canada).

Every attempt will be made to describe an adverse event in terms of a single diagnosis. If a clear diagnosis has been made, individual signs and symptoms will not be recorded. If a clear diagnosis cannot be established, each sign and symptom will be recorded individually. It should be noted that conditions necessitating surgical procedures may be considered adverse events if they satisfy the definitions above. The surgical procedure in question should be regarded as a therapeutic intervention rather than as an adverse event.

All participants who are deemed to have had a serious adverse event will be followed to determine the outcome. The clinical course of the adverse event will be followed up according to accepted standards of medical practice, even after the end of the study, until a satisfactory explanation is found or the investigator considers it medically justifiable to terminate follow-up.

### **6.3.4 Documentation and reporting of pregnancies and overdoses**

#### **6.3.4.1 Pregnancies**

Information on any pregnancies occurring during the study will be collected on specific forms and pregnancies will be followed to term. Any confirmed pregnancy will be reported within 1 working day of knowledge of the event, and study drugs will be stopped in concurrence with provision of follow-up medical care. Follow-up forms documenting the pregnancy outcome will also be completed.

#### **6.3.4.2 Overdoses**

Cases in which a “significant overdose” in the judgment of the investigator (for example, an overdose leading to severe hypoglycemia) of the study drug (insulin glargine, metformin or

Forxiga) was taken (regardless of whether or not any serious adverse event occurred) will also be reported on specific case report forms within 1 working day of knowledge of the event.

### **6.3.5 Period of observation**

For the purposes of this study, the period of observation for collection of adverse events, SAEs, overdoses and any pregnancies extends from the time the participant gives informed consent until the end of the study.

